8.2. SAS Code for Treatment Comparisons in MMRM

Note: The SAS code below is for MMRM after multiple imputations. For MMRM without imputations, use the same code for data before imputation without "by imputation ".

```
%let alpha=0.10;
data fcs2;
set fcs;
avisitn=40; CHG=cfb1; output;
avisitn=50; CHG=cfb2; output;
avisitn=60; CHG=cfb4; output;
avisitn=70; CHG=cfb6; output;
proc sort data=fcs2;
by _imputation_;
run;
proc mixed data=fcs2;
by _imputation_;
class GPN avisitn region usubjid;
```

model CHG=GPN base AVISITN GPN*AVISITN GPN*base region/alpha=&alpha DDFM = KR;repeated AVISITN/sub=usubjid type=UN; *** contrasts for treatment comparisons; lsmestimate GPN*AVISITN 'LSMean Active Pooled Visit 40' 0.5 0 0 0 0.5 0 0 0 0 0 0 0 0/CL alpha=α lsmestimate GPN*AVISITN 'LSMean Liafensine 1 mg QD Visit 40' 1 0 0 0 0 0 0 0 0 0 0 0 0/CL alpha=α lsmestimate GPN*AVISITN 'LSMean Liafensine 2 mg QD Visit 40' 0 0 0 0 1 0 0 0 0 0 0 0/CL alpha=α lsmestimate GPN*AVISITN 'LSMean Liafensine Placebo Visit 40' 0 0 0 0 0 0 0 0 1 0 0 0/CL alpha=α lsmestimate GPN*AVISITN 'Liafensine 1 mg QD vs. placebo Visit 40' 1 0 0 0 0 0 0 0 -1 0 0 0/CL alpha=α lsmestimate GPN*AVISITN 'Liafensine 2 mg QD vs. placebo Visit 40' 0 0 0 0 1 0 0 0 -1 0 0 0/CL alpha=α lsmestimate GPN*AVISITN 'Active Pooled vs. placebo Visit 40' 0.5 0 0 0 0.5 0 0 0 -1 0 0 0/CL alpha=α Ismestimate GPN*AVISITN 'LSMean Active Pooled Visit 50' 0 0.5 0 0 0 0.5 0 0 0 0 0 0/CL alpha=α lsmestimate GPN*AVISITN 'LSMean Liafensine 1 mg QD Visit 50' 0 1 0 0 0 0 0 0 0 0 0 0/CL alpha=α lsmestimate GPN*AVISITN 'LSMean Liafensine 2 mg QD Visit 50' 0 0 0 0 0 1 0 0 0 0 0 0/CL alpha=α lsmestimate GPN*AVISITN 'LSMean Liafensine Placebo Visit 50' 0 0 0 0 0 0 0 0 0 1 0 0/CL alpha=α lsmestimate GPN*AVISITN 'Liafensine 1 mg QD vs. placebo Visit 50' 0 1 0 0 0 0 0 0 0 -1 0 0/CL alpha=α lsmestimate GPN*AVISITN 'Liafensine 2 mg QD vs. placebo Visit 50' 0 0 0 0 0 1 0 0 0 -1 0 0/CL alpha=α lsmestimate GPN*AVISITN 'Active Pooled vs. placebo Visit 50' 0 0.5 0 0 0.5 0 0 0 -1 0 0/CL alpha=α Ismestimate GPN*AVISITN 'LSMean Active Pooled Visit 60' 0 0 0.5 0 0 0 0.5 0 0 0 0 0/CL alpha=α lsmestimate GPN*AVISITN 'LSMean Liafensine 1 mg QD Visit 60' 0 0 1 0 0 0 0 0 0 0 0 0/CL alpha=α lsmestimate GPN*AVISITN 'LSMean Liafensine 2 mg QD Visit 60' 0 0 0 0 0 0 1 0 0 0 0 0/CL alpha=α Ismestimate GPN*AVISITN 'LSMean Liafensine Placebo Visit 60' 0 0 0 0 0 0 0 0 0 1 0/CL alpha=α lsmestimate GPN*AVISITN 'Liafensine 1 mg QD vs. placebo Visit 60' 0 0 1 0 0 0 0 0 0 0 -1 0/CL alpha=α lsmestimate GPN*AVISITN 'Liafensine 2 mg QD vs. placebo Visit 60' 0 0 0 0 0 1 0 0 0 -1 0/CL alpha=α Ismestimate GPN*AVISITN 'Active Pooled vs. placebo Visit 60' 0 0 0.5 0 0 0 0.5 0 0 0 -1 0/CL alpha=α

Ismestimate GPN*AVISITN 'LSMean Active Pooled Visit 70' 0 0 0 0.5 0 0 0 0.5 0 0 0
0/CL alpha=α
lsmestimate GPN*AVISITN 'LSMean Liafensine 1 mg QD Visit 70' 0 0 0 1 0 0 0 0 0 0
0 0/CL alpha=α
lsmestimate GPN*AVISITN 'LSMean Liafensine 2 mg QD Visit 70' 0 0 0 0 0 0 1 0 0
0 0/CL alpha=α
lsmestimate GPN*AVISITN 'LSMean Liafensine Placebo Visit 70' 0 0 0 0 0 0 0 0 0 0 0 0 0 0 0 0 0 0
1/CL alpha=α
lsmestimate GPN*AVISITN 'Liafensine 1 mg QD vs. placebo Visit 70' 0 0 0 1 0 0 0 0 0
0 0 -1/CL alpha=α
lsmestimate GPN*AVISITN 'Liafensine 2 mg QD vs. placebo Visit 70' 0 0 0 0 0 0 1 0
0 0 -1/CL alpha=α
lsmestimate GPN*AVISITN 'Active Pooled vs. placebo Visit 70' 0 0 0 0.5 0 0 0 0.5 0 0
0 -1/CL alpha=α
lsmeans GPN*avisitn/CL alpha=α pdiff;
ods output diffs=diffs1 lsmeans=lsmean1 tests3=tests3 convergenceStatus=convg
LSMEstimates=LSM;
run;

8.3. SAS Code for Summarizing Treatment Comparison Results from Multiple Imputations Using Proc MIANALYZE

```
*** Analysis result from imputation and MIANALYZE - for CSR table;
%let alpha=0.10;
proc sort data=lsm;
by label _imputation_;
run;
proc mianalyze data=lsm alpha=α
by label ;
modeleffects ESTIMATE;
stderr stderr;
ods output ParameterEstimates=PARA;
run;
```

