5.4. Efficacy Analysis

All analyses will be presented for DGM4-positive, DGM4-negative, and both DGM4-positive and DGM4-negative subjects.

The analyses of the primary and key secondary efficacy endpoints will be conducted on the FAS. Supportive sensitivity analyses will be performed in the per protocol analysis set for primary and key secondary efficacy endpoints unless otherwise specified.

5.4.1. Primary Endpoint: Change in MADRS Total Score from Baseline to Day 42, in DGM4-Positive Patients

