In the analysis, data collected after initiation of prohibited medications will be used unless otherwise specified. All available data collected from all subjects before or after ICEs will be included in the analysis unless otherwise specified. Missing data due to any ICEs will be imputed using SAS MI procedure with the FCS statement and REGPMM option to implement the fully conditional specification method with predictive mean matching approach described in Section 5.4.1.1. For MADRS, the total score is set to missing if 50% or more items are missing at an assessment. When this occurs, the change from baseline value will be imputed without using any of the non-missing items.

The following variables will be included in the imputation model: region, baseline MADRS score, and change from baseline at Weeks 1, 2, 4, and 6. One hundred fully imputed datasets will be created. The MMRM described above will be used for treatment comparisons. Treatment effects (difference in LS means between treatment arms) from these 100 analyses will be combined to generate final results using Rubin's method implemented by SAS MIANALYZE procedure.

The following tables and figures will be generated to assess the MAR assumption:

- 1. A by-visit and overall summary table for (n, %), and cumulative (n, %) for reasons of missing value or early dropout in each arm due to:
 - AE including death
 - Withdrawal of consent to treatment discontinuation
 - Other reasons
 - Total (All of the above)

Within each arm, the summary statistics of the primary endpoint will also be generated by dropout reason at each visit. This table will also be used to support the figure below.

- 2. For each arm, generate a line graph for mean change from baseline (y-axis) over time (x-axis) by dropout reasons. There will be 4 lines on this figure to represent each dropout reasons:
 - None (completers)
 - Dropout due to AE including death
 - Dropout due to withdrawal of consent to treatment discontinuation
 - Dropout due to other reasons

In addition, a figure similar to the one above will be generated, with mean change from baseline replaced with a line graph for each subject. Subjects with the same reason for dropout will have the same color.

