8. APPENDIX: SAMPLE SAS CODES

The sample SAS codes provided in this section are for reference only. The actual SAS codes to generate the tables will be checked through QC process. For sensitivity analyses using RAS, use the dataset flag for RAS and exclude GPN*base, ie, treatment-by-baseline-score interaction, in the model statement in Proc Mixed.

8.1. SAS Code for Multiple Imputations Based on the Non-missing Values in the Same Arm with FCS and REGPMM Options

```
%let nimpute=100;
%let seed=10401;
proc sort data=adqs4 out=adqs5;
where avisitn in (40 50 60 70) and dgmn=1 and gpn^{3};
by trt01pn usubjid dgmn gpn region base avisitn;
run:
proc transpose data=adqs5 out=cfb;
 by GPN usubjid dgmn region base;
 var chg;
 id avisitn;
run;
*** Imputation using fully conditional specification and predictive mean matching methods;
proc mi data=cfb(rename=( 40=cfb1 50=cfb2 60=cfb4 70=cfb6)) nimpute=&nimpute
seed=&seed out=fcs;
 by GPN;
 class region;
 var region base cfb1 cfb2 cfb4 cfb6;
 FCS REGPMM;
run:
```

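### The sample pooling code drops the Kenward-Roger degrees of freedom, so imputed comparisons use almost normal critical values; the effect on the primary test is about 0.1 to 0.2 percentage points

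*SAP*

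**What the plan says.** SAP 5.4.1.2 (Main Estimator) makes the primary analysis an MMRM on 100 imputed datasets, combined by "Rubin's method implemented by SAS MIANALYZE procedure". It names no rule for the degrees of freedom of the pooled test.

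The sample code fills in the detail:

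- Appendix 8.1 sets "let nimpute=100".
- Appendix 8.2 fits the model to each imputed dataset with an unstructured covariance and "region/alpha=&alpha DDFM = KR". It sends the contrasts to a dataset through "LSMEstimates=LSM".
- Appendix 8.3 pools with "proc mianalyze data=lsm" and an alpha of 0.10, run by contrast label. It reads "modeleffects ESTIMATE" and "stderr stderr". No EDF= option appears, and the degrees of freedom of the individual fits are not used.

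The opening of Appendix 8 says that the code is for reference only and that the production code will go through quality control.

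Two passages bear on how far the point reaches. SAP 5.4 says "All analyses will be presented for DGM4-positive, DGM4-negative, and both DGM4-positive and DGM4-negative subjects". SAP 5.6.4 says that the MADRS change in DGM4-negative patients will be summarised descriptively.

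**The concern.** Kenward-Roger does two things in a small sample: it adjusts the standard error and it supplies denominator degrees of freedom. The first reaches the pooling step and the second does not. Without EDF=, PROC MIANALYZE takes the complete-data degrees of freedom as infinite. The only limit left is the number of imputations, and 100 imputations make that limit very loose. The pooled test is then close to a z-test, although the plan asked for a small-sample method in each fit.

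Three consequences follow.

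- The pooled primary test uses a slightly lenient critical value.
- The MMRM without imputation (SAP 5.4.1.3, second sensitivity analysis) is there to show what imputation does. It reuses the Appendix 8.2 code and keeps its KR degrees of freedom. Primary and comparator would therefore differ in reference distribution for a reason unrelated to imputation.
- The tipping-point analyses, which turn on where significance is lost or gained, also pool through Appendix 8.3.

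**Working it through.** **Inputs from the documents.** m = 100 imputations (SAP 5.4.1.2, Appendix 8.1). About 150 DGM4-positive patients, 50 per arm, and about 30 DGM4-negative patients, 10 per arm; SD 9; 47 per arm to detect 4.5 points with 80% power at two-sided 0.05 (all SAP 2.3). One-sided alpha 0.05 (SAP 3.7). 90% intervals (Appendices 8.2 and 8.3).

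**Assumptions, because the documents give no figure.** The fraction of missing information λ is taken as 2% to 50%. The complete-data degrees of freedom ν0 are taken as 134 to 147 in DGM4-positive patients (150 less 16 to 3 parameters) and 21 to 27 in DGM4-negative patients.

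**The plan's own figure.** The plan states no degrees of freedom or critical value, so the only figure to reproduce is the sample size. With 47 placebo and 94 active patients, SE = 9 × √(1/47 + 1/94) = 1.608 and 4.5/1.608 = 2.799. Power is Φ(2.799 − 1.960) = 79.9%, or 79.4% by noncentral t. Dividing by 0.95, 47/0.95 = 49.5, which rounds up to 50. The sizing reproduces, and this point does not touch it.

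**Step 1: default pooled degrees of freedom.** ν_m = (m − 1)/λ².

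- λ = 2%: 99/0.0004 = 247,500
- λ = 20%: 99/0.04 = 2,475
- λ = 50%: 99/0.25 = 396

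The one-sided 5% critical values are 1.645 to 1.649, against z = 1.645.

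**Step 2: small-sample (Barnard-Rubin) degrees of freedom.** ν_obs = ν0 × (ν0 + 1)/(ν0 + 3) × (1 − λ), and the pooled value is 1/(1/ν_m + 1/ν_obs).

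Example with ν0 = 143 and λ = 20%: ν_obs = 143 × 144/146 × 0.8 = 112.8, and 1/(1/2,475 + 1/112.8) = 107.9. The critical value is 1.6591 instead of 1.6455, so the interval is 0.8% wider.

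**Step 3: size of the effect.** Actual level is the probability that a t variable with the Step 2 degrees of freedom exceeds the default critical value.

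| Population | λ | Default critical value | Small-sample critical value | Extra 90% interval width | Actual level at one-sided 5% |
|---|---|---|---|---|---|
| DGM4-positive, ν0 134–147 | 2%–50% | 1.645–1.649 | 1.656–1.672 | 0.7%–1.4% | 5.11%–5.24% |
| DGM4-negative, ν0 21–27 | 2%–30% | 1.645–1.646 | 1.709–1.768 | about 4%–7% | 5.6%–6.2% |

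At one-sided 0.025, the level in the protocol, the DGM4-positive range is 2.60% to 2.71%.

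**In MADRS points.** At SD 9 with 100 versus 50 patients, SE = 9 × √(1/100 + 1/50) = 1.559. The half-widths are 1.559 × 1.6455 = 2.565 and 1.559 × 1.6591 = 2.586, a difference of about 0.02 points.

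**Simulation.** Simplified null simulations of a Day 42 comparison (50 per arm, about 20% missing, not the full MMRM) gave these one-sided rejection rates at nominal 5%:

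- Normal-model imputation: 4.90% with default and 4.74% with small-sample degrees of freedom in a run of 20,000 trials (Monte Carlo standard error about 0.15 points); about 4.7% and 4.5% in a separate run.
- Predictive mean matching within arm, as the SAP specifies: about 5.6% and about 5.5%.

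In each case the missing degrees of freedom account for 0.1 to 0.2 points, in line with the formula. Whether the total lies above or below 5% depends more on the imputation method.

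**The case against.** The strongest reply is that this is a refinement and not an error. The governing text asks only for Rubin's method through PROC MIANALYZE, and the default call delivers that. The code is sample code. At about 150 patients the effect is trivial, and normal-model simulation showed no rejection rate above 5%. The MMRM without imputation, which is also the basis for the key secondary endpoint (SAP 5.4.2), keeps KR inference in full.

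Most of this stands, and it sets the size of the point. It does not remove the point. SAP 5.4.1.2 and 5.4.1.3 send the reader to the appendix for implementation, a comment in Appendix 8.3 marks its output as being for the study report table, and no other section supplies a rule.

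Three stronger readings are tempting, and the documents do not support them.

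- *That the whole KR correction is lost.* It is not. The pooled standard error comes from the KR fit, so its adjustment carries through.
- *That the primary test is materially anti-conservative.* The shift is 0.1 to 0.2 percentage points. It could change a conclusion only for a p-value that close to the threshold.
- *That the DGM4-negative intervals will be visibly too narrow.* This needs the general sentence in SAP 5.4 to be read as requiring the imputed MMRM in that group. The section on that endpoint, SAP 5.6.4, is descriptive, and the sample imputation code selects DGM4-positive patients only. The code also produces 90% intervals, so a comparison of 95% critical values would not describe the planned output.

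**Conclusion.** The point holds as a minor correction. As written, the sample code loses the KR degrees of freedom, and the SAP text does not replace them. Under the assumed missing information and complete-data degrees of freedom, the DGM4-positive intervals fall short by roughly 1% of their width, and the nominal one-sided 5% corresponds to about 5.1% to 5.2%. The direction is certain; the exact size depends on λ, which the documents do not give. Sample size and point estimates are unaffected.

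The 4% to 7% shortfall in DGM4-negative patients is conditional on an analysis that the SAP's specific section does not plan. SAP 5.4 and 5.6.4 should be reconciled in any case. The practical reason to act is to fix the rule before unblinding, so that it is not chosen after a p-value has landed near the threshold, and to put the primary analysis and its non-imputed comparator on the same footing.

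**What to change.** In SAP 5.4.1.2, state that pooled tests and intervals use the small-sample (Barnard-Rubin) degrees of freedom, with the complete-data value taken as the mean KR degrees of freedom of that contrast over the 100 imputed datasets.

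In Appendix 8.3, supply this through EDF=. The option takes one number per call, while the present call processes all contrasts by label. So either run one PROC MIANALYZE call per contrast, or use one conservative common value, such as the smallest mean KR degrees of freedom among the contrasts. The tipping-point and control-based analyses pick up the change because they pool through the same code.

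The cost is slightly larger p-values, slightly wider intervals and a short loop or a few extra calls. No new data are needed.

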8.4. SAS Code for Imputation Using Non-missing Values in the Control Arm

proc sort data=adqs4 out=adqs5 ; where avisitn in (40 50 60 70) and dgmn=1 and gpn^=3; by trt01pn usubjid dgmn gpn region base avisitn; run; proc transpose data=adqs5 out=cfb; by GPN usubjid dgmn region base; var chg; id avisitn; run;

*** Pattern-Mixture imputation using fully conditional specification and predictive mean matching methods; proc mi data=cfb(rename=(40=cfb1 50=cfb2 60=cfb4 70=cfb6)) nimpute=&nimpute seed=&seed out=fcs; class gpn region; FCS REGPMM; mnar model(cfb1 cfb2 cfb4 cfb6/modelobs=(gpn='4')); *** gpn='4': control arm; var region base cfb1 cfb2 cfb4 cfb6; run: data fcs2; set fcs; avisitn=40; CHG=cfb1; output; avisitn=50; CHG=cfb2; output; avisitn=60; CHG=cfb4; output; avisitn=70; CHG=cfb6; output; proc sort data=fcs2; by imputation ; run:

8.5. SAS Code for Imputation Using Non-missing Values in the Control Arm or the Same Arm per Intercurrent Events

The SAS code will follow the algorithm below.

- Pool subjects who terminated early due to AE in all 3 arms and subjects in the placebo arm. This dataset will also include placebo subjects with missing values due to withdrawal of consent to treatment, other/lost to follow-up, or pregnancy, but will exclude early terminators due to death.
- 2) For the pooled datasets in 1), use sample SAS code below to impute missing values based on non-missing values in the place arm to create 100 datasets.

```
proc mi data=cfb0(rename=(_40=cfb1 _50=cfb2 _60=cfb4 _70=cfb6))
nimpute=&nimpute seed=&seed out=ras0;
class gpn region;
FCS REGPMM;
mnar model(cfb1 cfb2 cfb4 cfb6/modelobs=(gpn='4'));
**** gpn='4': control arm;
```

- 3) Select subjects in the 1 mg group by excluding early terminators due to AE or death. This dataset will include subjects without missing values and subjects with missing values due to withdrawal of consent to treatment, other/lost to follow-up, or pregnancy.
- 4) For the datasets in 3), use sample SAS code below to impute missing values based on non-missing values in the same arm to create 100 datasets.

```
proc mi data=cfb1(rename=(_40=cfb1 _50=cfb2 _60=cfb4 _70=cfb6))
nimpute=&nimpute seed=&seed out=ras1;
class nonm region;
```

```
FCS REGPMM;
mnar model(cfb1 cfb2 cfb4 cfb6/modelobs=(nonm='1'));
***Variable nonm=1: completers;
var region base cfb1 cfb2 cfb4 cfb6;
run;
```

- 5) Repeat steps 3) and 4) for the 2 mg group and name the imputed datasets as ras2.

8.6. SAS Code for Imputation Pertaining to Use of Prohibited Medications

In Sensitivity analysis 3 in Section 5.4.1.3, data collected after initiation of prohibited medications will not be used. They will be imputed using non-missing values in the placebo arm. SAS code in Section 8.4 will be used.

In Sensitivity analysis 4 in Section 5.4.1.3, data after initiation of prohibited medication will be imputed with non-missing data in the same arm while the subject is on study medication. If the subject terminates study medication early after initiation of prohibited medication, missing data after treatment termination will be imputed according to the cause of termination. Two scenarios may occur as follows:

 The subject initiated prohibited medication and completed the treatment period. Imputation of data after initiation of prohibited medication will be the same as imputing missing data in Group 2 in Sensitivity analysis 4, and the SAS code in Section 8.5 will be applied.

- 2) The subject initiated prohibited medication and terminated the treatment early. If the cause of termination is in Group 2 in Sensitivity analysis 4, the imputation will be same as in 1). If the reason for termination is in Groups 1 or 3, the following steps will be followed.
 - a. Impute data after initiation of prohibited medication as in 1).
 - b. Set imputed data after termination as missing.
 - c. If the cause of termination is death, impute data using the method stated in 6) in Section 8.5.
 - d. If early termination is due to AE, perform a second set of imputation for data after early termination based on non-missing data in the placebo arm.

8.7. SAS Code for Tipping Point Analysis

The SAS code will follow the algorithm below.

- 1) Impute missing values per SAP to create 100 datasets.
- 2) In each dataset, create a variable MIFL (imputation flag) to indicate whether a data point was imputed or not.
- 3) Increase or decrease each imputed value per macro parameter for each arm.
- 4) For each dataset, perform treatment comparisons using LSMESTIMATE statements in Proc Mixed.
- 5) Use Proc MIANALYZE to summarize the final result from the analysis of the 100 datasets.

%macro Tipping(indata=, cfb=, gp1=, gp2, gp4=, outdata=);

*** Indata=input dataset from steps 1) and 2) above. For each imputed dataset, the data structure should be one observation per subject per visit.

Cfb=variable name for change from baseline value gp1=imputed data to be shifted in the 2 mg arm gp2=imputed data to be shifted in the 1 mg arm gp4=imputed data to be shifted in the placebo arm outdata=output dataset for the final result from Proc MIANALYZE; data a; set & indata: if MIFL='Y' then do: if GPN=1 then &cfb=&cfb + (&gp1); else if GPN=2 then &cfb=&cfb + (&gp2); else if GPN=4 then &cfb=&cfb + (&gp4); end: *** Include SAS code in Section 8.2 to perform treatment comparisons. *** Include SAS code in Section 8.3 to use Proc MIANALYZE to summarize the final result from the analysis of the 100 datasets and output the final result to dataset &outdata.

%mend;

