8.8. SAS Code for Stratified CMH Test

*** CMH test for pooled analysis stratified by region;

- *** gpn=3: both active arms pooled, gpn=4: placebo arm;
- *** For 1 mg vs. placebo and 2 mg vs. placebo, replace 3 with 1 and 2, respectively.;
- proc freq data=adqs4(where=(gpn in (3 4) and dgmn=3 and avisitn=70));
- table region*GPN*aval / CMH ALPHA=0.10;

run;

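### SAP 8.7 names the two dose shifts in the reverse of the arm coding used in 8.2, 8.8 and 5.4.1.2, so dose-specific tipping runs that follow those definitions would shift the other dose arm

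*SAP*

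**What the plan says.** **Model code (SAP 8.2).** The dose contrasts are written as coefficient vectors over GPN by visit. The Day 7 lines are "Liafensine 1 mg QD vs. placebo Visit 40' 1 0 0 0 0 0 0 0 -1 0 0 0/CL" and "Liafensine 2 mg QD vs. placebo Visit 40' 0 0 0 0 1 0 0 0 -1 0 0 0/CL". The same pattern is repeated at the later visits.

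**Levels that reach the model.** The data step in 8.4 keeps "where avisitn in (40 50 60 70) and dgmn=1 and gpn^=3", and 8.8 explains the codes as "gpn=3: both active arms pooled, gpn=4: placebo arm". The model therefore sees GPN levels 1, 2 and 4.

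**CMH code (SAP 8.8).** The instruction is "For 1 mg vs. placebo and 2 mg vs. placebo, replace 3 with 1 and 2, respectively".

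**Main text (SAP 5.4.1.2).** The hypotheses index the arms in the order 1 mg, 2 mg, pooled.

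**Tipping macro (SAP 8.7).** The parameters are defined as "gp1=imputed data to be shifted in the 2 mg arm gp2=imputed data to be shifted in the 1 mg arm". The executable lines begin "if GPN=1 then &cfb=&cfb + (&gp1" and go on to add gp2 to GPN=2 and gp4 to GPN=4. The macro then calls the 8.2 code for the treatment comparisons.

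**Tipping rules (SAP 5.4.1.3).** There are three variants: shift the active arm, shift placebo, or shift both. Only the arms under test are shifted. In the pooled analysis each dose arm gets its own shift. Significance means significance after multiplicity adjustment.

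**The concern.** The parameter definitions in 8.7 imply that GPN=1 is 2 mg. Everything else in the SAP that bears on the coding implies that GPN=1 is 1 mg. Because 8.7 runs the 8.2 contrasts inside the macro, the two readings meet in one program.

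The mistake would be silent. The program runs, the shift is applied to the dose arm that is not being tested, and the tested difference stays where it was. Section 5.4.1.3 treats the need for a large shift as evidence of robustness, so the error runs towards false reassurance. The dose comparisons are formal steps in the closed test of SAP 3.7. The tipping procedure is used again for the control-based imputation and in the randomized analysis set, so the same slip could recur in several outputs.

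**Working it through.** **1. Coding check.** With GPN levels 1, 2, 4 and four visits, the twelve coefficients fall in three blocks of four. This assumes GPN is sorted by its numeric value, with no format that reorders it.

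| Place | GPN=1 | GPN=2 |
|---|---|---|
| 8.2 contrast vectors | 1 mg | 2 mg |
| 8.8 comment | 1 mg | 2 mg |
| 5.4.1.2 index order | 1 mg | 2 mg |
| 8.7 definitions of gp1, gp2 | 2 mg | 1 mg |

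The executable lines in 8.7 pair gp1 with GPN=1 and gp2 with GPN=2 and name no dose. Only the definitions are reversed.

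**2. Effect on the estimate.** Let *m* be the imputed fraction and *d* the shift. Shifting the tested arm moves the dose contrast by *m·d*; shifting the other dose arm moves it by 0. With a difference of −4.5, *m* = 0.20 and *d* = +10, the contrast should go to −4.5 + 0.20×10 = −2.5, but it stays at −4.5.

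**3. Effect on the tipping point.** The plan gives no tipping figure to reproduce. The inputs are 50 per arm and SD 9 (SAP 2.3), 1-sided alpha 0.05 (SAP 3.7), an illustrative observed effect of 5.0, and *m* = 10% to 30%. The imputed fraction is an assumption, because the documents give none. The model is an unadjusted three-arm Day 42 comparison with pooled variance, not the planned MMRM with multiple imputation. The critical t on 147 df is 1.655. The result tips at the smallest whole *d* for which

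effect − *k·m·d* ≤ 1.655 × √[(2/50) × (81 + (*a*/3)·*m*(1−*m*)·*d*²)]

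Here *a* is the number of arms shifted. For active-only, *a* = 1, with *k* = 1 for the right arm and 0 for the wrong arm. For active plus placebo, *a* = 2, with *k* = 2 for the right arm and 1 for the wrong arm.

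Example at *m* = 0.10, active-only:
- Right arm, *d* = 19: 5.0 − 1.9 = 3.10 against 3.17, so it tips (at 18: 3.20 against 3.15, so it does not).
- Wrong arm, *d* = 71: 5.0 against 5.04, so it tips only because the pooled variance has grown.

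| Variant | Arm shifted | *m* = 10% | 15% | 30% |
|---|---|---|---|---|
| Active only | right | 19 | 13 | 7 |
| Active only | wrong | 71 | 59 | 46 |
| Active + placebo | right | 10 | 7 | 4 |
| Active + placebo | wrong | 18 | 13 | 7 |
| Placebo only | not affected | 19 | 13 | 7 |

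**4. Multiplicity gate.** The figures above use the dose contrast's own p-value. If the pooled test is redone at each step, as the adjusted-significance rule suggests, the wrong-arm run stops earlier, because the pooled contrast does move, by 0.5·*m·d*. Assume a pooled effect of 5.0 as well. The pooled variance factor is (0.25 + 0.25 + 1)/50 = 0.03, and the condition becomes

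5.0 − 0.5·*m·d* ≤ 1.655 × √[0.03 × (81 + (1/3)·*m*(1−*m*)·*d*²)]

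This is met at *d* = 37, 27 and 15 for *m* = 10%, 15% and 30%. That is still about twice the right-arm values of 19, 13 and 7.

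**5. Pooled analysis.** The pooled contrast weights each dose 0.5, so relabelling the doses leaves the unshifted primary test unchanged. In pooled tipping, a shift in either dose arm moves the estimate equally if the imputed fractions are equal (with *m* = 0.20 and *d* = 10, −4.5 + 0.5×0.20×10 = −3.5 either way). Only the name of the shifted dose would be wrong.

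**The case against.** The strongest reply is that Section 8 opens by saying its code is illustrative and that production code will go through QC. That stands: the harm is conditional on someone passing shifts by the printed definitions. It does not dispose of the point. QC compares programs with a specification, and here the specification holds both mappings with no code list to choose between them.

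It is also fair that the executable lines are consistent with 8.2 and 8.8, and that the results could give the error away. Placebo-only tipping is correct in any case and would sit at 19 to 7 points beside an active-only result of 71 to 46. Section 5.4.1.3 also asks for up to three results before the tipping point, and these would show an estimate that is not moving. An attentive reviewer would probably notice.

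A reader might infer something stronger: that 8.7 holds the true coding, so that 8.2 and 8.8 label the doses the wrong way round and efficacy would be credited to the wrong dose. The documents do not support this. Three places agree on 1 mg first and one set of definitions disagrees. No code list excludes the stronger reading formally, but nothing beyond that one line points to it. Nor can one conclude that the tipping analysis will shift the wrong arm, only that it would if the definitions were followed unchecked.

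**Conclusion.** The inconsistency is certain from the text, and 8.7 is wrong as written relative to the rest of the SAP. Its consequence is limited and conditional. If shifts are passed by the printed definitions, dose-specific active-only tipping is overstated several-fold on the dose contrast's own p-value, and about two-fold if the pooled gate is retested. Active-plus-placebo tipping is overstated by a little under two-fold. Placebo-only tipping and the unshifted pooled primary test are untouched. In pooled tipping the shifted dose would be misnamed.

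The sizes rest on an assumed imputed fraction, an assumed observed effect and a simplified Day 42 test. The direction does not depend on those choices. Severity: minor.

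**What to change.** State the GPN code list once at the head of SAP Section 8 (the dose for 1, the dose for 2, 3 = pooled, 4 = placebo), verify it against the analysis dataset specification, and make 8.2, 8.7 and 8.8 agree with it. On the weight of the text, this most likely means changing the 8.7 definitions so that gp1 is the 1 mg shift and gp2 the 2 mg shift, with the executable lines left alone. Add a programming check that, after each tipping run, the imputed values have changed by the stated amount in the named arm or arms and in no other.

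The cost is a few lines of appendix text and one automated check. No analysis, sample size or timeline changes.
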